Molar Incisor Hypomineralization (MIH) is a systemic origin, qualitative developmental defect of enamel affecting one to four first permanent molars and frequently involving incisors (Weerheijm, 2001). Lesion presented as well-demarcated discolouration of the enamel, or enamel destruction due to breakdown or dental caries with a global prevalence was estimated around 14.2% (Schwendicke F et al, 2018). MIH teeth presented with various clinical problem including increase susceptibility of caries and post eruptive breakdown, inferior bonding to composite restoration, recurrent restorative failure, hypersensitivity, and difficulty to achieve anaesthesia. Extraction of the MIH affected first permanent molar is an option and require comprehensive evaluation and 'ideal' time. Currently, acceptance to invasive restorative treatment and extraction is a significant challenge in children. Hence, a less-invasive treatment using glass ionomer cement (GIC) with remineralisation and desensitising agents that comply with principle of Minimal Intervention Dentistry (MID) has gained attention as interim therapeutic restoration in moderate to severe MIH affected tooth to prevent progression of disease. Silver Diamine is a high concentration topical fluoride agent has shown superior performance for remineralization and caries arrest (Gao et al., 2016). Papain based gel is a chemomechanical caries removal and deproteinizing agent assist to remove debris and protein without the need of rotary instrument(Deng et a., 2018). There is a paucity in the published literature regarding the effect of SDF and papain-based gel on MIH-affected teeth. To date, no study has been done to evaluate the clinical outcome of MIH-affected molars treated with papain-based gel as deproteinising agent and SDF followed by interim therapeutic restoration with GIC. It is hoped that findings obtained from this study will give new insight into managing MIH-affected molars in children

Objective:

The aim of the study is to determine the clinical outcome of additional SDF with and without papain-based gel on MIH molars versus HVGIC alone as interim therapeutic restoration at 6 and 12 months. Specifically, the objective of this study is

1. To determine and compare the clinical outcome determine as success and failure of treatment related to pulpal health, structural integrity and hypersensitivity on MIH molars treated with GIC alone or with or without the use of SDF and papain-based gel at 6 and 12 months

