Sample size: The sample size is calculated based on Grossi et al., who reported that the clinical success of GIC (Equia Forte) restoration using ART technique in MIH affected permanent molars was 98.3% (Grossi et al., 2018). Since there was no literature reporting on the clinical success of Silver Diamine Fluoride and papain-based gel on MIH-affected molars, the success rate was assumed to be 50%. With an estimated error of 5% and power of 90%, the minimum estimated sample size was calculated to be 14 teeth per intervention group. The sample size calculation will be performed using G-power 3.1 software that calculated the power and sample size for tests by comparing two independent binomial populations with probabilities π_1 and π_2 , respectively. Pearson chi-square test was used to test the association of two binary variables (two groups and two outcomes). An additional 50% was added to compensate for the possibility of high dropout or recall failure. Hence, the number was increased to 21 teeth per group for a total of 63 teeth. The high percentage of dropout rate in this study is decided to accommodate a high need of retreatment of GIC restoration based on few published literature (Al Muallem et al., 2018; Linner et al., 2020). Besides, the high dropout rate may also be related to the higher chance of the affected molar to be extracted following advice by an orthodontist during the review phase.

Data Management and Analysis:

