Data obtained will be entered and analysed using Statistical Package for the Social Sciences (SPSS) version 26.0 software. The continuous data will be checked for normality of distribution and reported accordingly. Categorical data in this study are the clinical parameters, clinical outcome, and restorative quality. Descriptive statistics of frequencies and percentages will be presented for categorical data. The primary data analysis will be done using Intention-to-treat (ITT) analysis involving all the samples recruited and randomised. The Per Protocol (PP) analysis will be done to compare the difference between treatment effects as a sensitive analysis of missing value. Comparison of categorical outcomes will be assessed using Chi-square goodness of fit test and Friedman Two-way Analysis of Variance (ANOVA) by Ranks test. Association studies such as factors affecting the outcome will be further evaluated using the Binary Logistic Regression. In all analyses, the level of significance is set at $p<0.05$. The power of the study will be calculated using G*Power Version 3.1.9.4 using the Post Hoc test of Goodness-of-Fit.

Ethical Consideration:

This study has already received approval from the Medical Ethics Committees, Faculty of Dentistry, University of Malaya (CD1912/0061/20155(P)). Patient Information Sheet (PIS) will be disseminated to parents and participated children before consenting. Written informed and verbal consent from parents and, where appropriate, the children, were obtained before intervention. Participation is based on a voluntary basis and they may decide to leave at any time of the study.

Reference:

1. Almualllem, Z. & Busutil-Naudi, A. 2018. Molar incisor hypomineralisation (MIH) – an overview. *British Dental Journal*, 225, 601-609.
4. Gao, S. S., Zhang, S., Mei, M. L., Lo, E. C.-M. & Chu, C.-H. 2016. Caries remineralisation and arresting effect in children by professionally applied fluoride treatment – a systematic review. *BMC Oral Health*, 16.

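### The tests named for categorical outcomes (chi-square goodness of fit and Friedman) are not tests of association between three independent arms and success/failure, and they conflict with the Pearson test used to size the trial

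*Combined protocol and SAP*

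**What the plan says.** The Study Design paragraph describes a parallel trial with three arms, and teeth are randomised 1:1:1 in blocks. The first specific objective is "To determine and compare the clinical outcome determine as success and failure of treatment" at 6 and 12 months.

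The Data Management and Analysis section first classes the outcome: "Categorical data in this study are the clinical parameters, clinical outcome, and restorative quality". It then assigns the tests: "Comparison of categorical outcomes will be assessed using Chi-square goodness of fit test and Friedman Two-way Analysis of Variance (ANOVA) by Ranks test". No other sentence gives a test for comparing success and failure between arms. Three nearby statements come close:

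- The per-protocol sentence mentions treatment effects but names no test: "The Per Protocol (PP) analysis will be done to compare the difference between treatment effects as a sensitive analysis of missing value".
- Logistic regression is planned, but arm is not stated as a term: "Association studies such as factors affecting the outcome will be further evaluated using the Binary Logistic Regression".
- The section ends by basing a post hoc power calculation on goodness of fit.

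The Sample size section uses a different test: "Pearson chi-square test was used to test the association of two binary variables (two groups and two outcomes". Its inputs are a cited study that "reported that the clinical success of GIC (Equia Forte) restoration using ART technique in MIH affected permanent molars was 98.3"%, an assumed 50% for the new treatments, 5% error and 90% power. They give 14 teeth per group, raised to 21 per group and 63 in total.

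**The concern.** A goodness-of-fit test sets one set of counts against a distribution fixed in advance. The plan states no such distribution, so the analyst would have to choose one, possibly after seeing the data. A Friedman test ranks related measurements within a unit. It can address 6- v 12-month change in the same tooth. It could compare arms only if every child supplied a matched tooth to each arm, and the design requires only one affected molar per child.

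The main comparison is therefore tied to two procedures, one undefined as written and the other meant for a different question. The quoted 90% power belongs to a third test that the analysis section does not mention. At stake are the pre-specification of the main result and, under some readings, much of the power.

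**Working it through.** **Inputs.** Success 98.3% (GIC) and 50% (new treatments), 5% error, 90% power, and 14 or 21 teeth per group, all from the Sample size section. Sidedness is not stated there, so two-sided is assumed. Both new arms are taken at 50%.

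**1. Reproducing 14 per group.** With p1 = 0.983, p2 = 0.5 and mean 0.7415, the pooled two-sided formula is

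n = [1.960·√(2·0.7415·0.2585) + 1.282·√(0.983·0.017 + 0.5·0.5)]² / 0.483² = (1.214 + 0.662)² / 0.2333 ≈ 15.1, so 16.

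The unpooled and arcsine versions both give 13. Exact power of the uncorrected 2x2 Pearson test is 90.1% at 13 and 92.7% at 14. The stated 14 is thus consistent with a two-group Pearson test. Then 14 × 1.5 = 21 and 21 × 3 = 63.

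**2. What goodness of fit could mean.** Let x_i be the successes in arm i, n the teeth per arm, m the mean of the x_i, and SS = Σ(x_i − m)². Three readings have 2 df (critical value 5.99):

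- success counts against equal counts: SS/m
- failure counts against equal counts: SS/(n − m)
- all six arm-by-outcome cells, with expected counts from the pooled success rate: SS/m + SS/(n − m)

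The third is algebraically the 3x2 Pearson statistic. Each of the first two is one part of it, so neither can exceed it.

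**3. Example.** Take 21, 10 and 11 successes out of 21. Then m = 14 and SS = 7² + 4² + 3² = 74.

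- Success counts: 74/14 = 5.29, p = 0.071.
- Failure counts: 74/7 = 10.57, p = 0.005.
- Six cells (Pearson): 15.86, p = 0.0004.

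**4. Power**, by exact enumeration of all (n+1)³ outcomes. The 90% control rate is an assumption. It is included because the Sample size section also expects to "accommodate a high need of retreatment of GIC restoration", so 98.3% may be optimistic.

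| Success rates | Teeth per arm | Success counts | Failure counts | 3x2 Pearson |
|---|---|---|---|---|
| 98.3/50/50 | 14 | 12.4% | 77.5% | 93.7% |
| 98.3/50/50 | 21 | 39.3% | 97.6% | 99.6% |
| 90/50/50 | 14 | 6.9% | 36.5% | 68.5% |
| 90/50/50 | 21 | 20.2% | 65.4% | 87.5% |

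**5. Rejection rate when all arms are equal**, at 14/21 per arm:

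| Common success | Success counts | Failure counts | 3x2 Pearson |
|---|---|---|---|
| 50% | 0.3%/0.3% | 0.3%/0.3% | 4.5%/5.6% |
| 80% | 0.0%/0.0% | 2.2%/2.5% | 4.0%/5.1% |
| 90% | 0.0%/0.0% | 3.1%/3.1% | 3.4%/4.0% |

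Both single-count readings fall below the nominal 5%, and the success-count reading is far below it throughout.

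**The case against.** The strongest defence is a naming slip. The Sample size section states a suitable test, the six-cell reading of goodness of fit is that test extended to three arms, and the second mention of goodness of fit may be only a label from the power software. On that view nothing is lost except clarity. This stands as a possibility. It does not remove the need for a correction, because the wording appears twice, no expected distribution is given, and even the Sample size section covers only two groups.

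With 1:1:1 allocation, equal counts per arm are also a natural null, so goodness of fit can be made to compare arms after a fashion. That is right, and it is why the loss is given as a range. Friedman has a legitimate use for the two visits. Logistic regression could also carry an arm term; the plan does not exclude it, but does not state it either.

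A reader might infer more than the documents support:

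- That the trial will have only 12% or 39% power. That holds for one reading of an unspecified test; another loses nothing.
- That the sample size is wrong. The 14 per group is consistent with its own two-group test.
- That the stated 90% covers a three-arm comparison. Only a two-group calculation was described.

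Clustering of teeth within a child, and logistic regression when an arm has no failures, are separate questions and do not bear on this point.

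**Conclusion.** The point holds as a conflict between the Sample size and Data Management and Analysis sections, and as a wrong or incomplete specification of the main comparison. Neither named test, as written, is a test of association between three independent arms and success/failure.

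The power loss at the planning rates runs from none (six cells, 2 df), through 16 percentage points at 14 teeth per arm and 2 at 21 (failure counts), to 81 and 60 points (success counts). These figures assume independent teeth, equal arms, a two-sided 5% level and 50% success in both new arms. The conclusion that the text must be corrected depends on none of them. It should be settled before outcome data are seen.

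**What to change.** Replace the sentence that assigns tests to categorical outcomes with:

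> Success/failure at 12 months (and, secondarily, at 6 months) will be compared between the three randomised arms with a 3x2 Pearson chi-square test of independence, or the Fisher-Freeman-Halton exact test if any expected count is below 5, two-sided 0.05. Pairwise 2x2 comparisons (Fisher exact if any expected count is below 5) are made only if the global test is significant. Friedman (or Cochran Q) is used only for within-tooth change between visits.

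Twelve months is proposed as primary because the Study Summary points to it. The exact alternative matters: at the planning rates with 14 teeth per arm, expected failures per arm are (14 × 0.017 + 7 + 7)/3 ≈ 4.7. Global power with this rule is 93.0% at 14 and 99.6% at 21.

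Delete the post hoc goodness-of-fit power. State instead that the 90% refers to the two-group 2x2 Pearson test (exact power 92.7% at 14 per group), not to the three-arm test or the gated pairwise contrasts.

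**Cost.** This is a change of wording, and 63 teeth can stay. The downside is that pairwise tests become conditional on the global test. At 14 evaluable teeth per arm, control v one arm then has 83% power, and both control contrasts together 72.5%; at 21 these are 98% and 96.5%. With all arms equal at 50% to 90% success, the chance of any false pairwise claim is at most 4.4% at 14 and 5.6% at 21, against up to 9.0% and 13.3% without the gate.

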Methodology:

Study Design: This study is a single centre, three arms, parallel randomised controlled trial (RCT) on MIH molars in children aged 5 to 15-year-old presented with at least one molar tooth diagnosed as MIH. RCT was opted as it allows comparison of data with the conventional management using GIC which is a common interim therapeutic restorative material of choice.

Research Subject and Participant: MIH screening and diagnosis of the first permanent molar will be done using the European Academy of Paediatric Dentist (EAPD) MIH index by Ghanim et al., 2015, ICDAS caries assessment, clinical assessment, and radiographic evaluation. The inclusion criteria of the participant and molar include.

1. Children aged 5 – 15 years old
2. Healthy with no medical problem
3. Subject presented with at least one MIH FPM with:
 - a. Post eruptive breakdown (PEB)
 - b. Unsatisfactory atypical restoration
 - c. Atypical caries without pulp involvement

The exclusion criteria of the participant and molars include

1. Children with difficulty comprehending instruction
2. Children with inability to perform oral hygiene care independently
3. Known allergy to silver
4. Affected FPM with
 - a. Non MIH defect (Fluorosis, Amelogenesis Imperfecta)
 - b. No PEB and carious lesion
 - c. Lesion into the pulp

- d. Intact restoration
- e. Extensive coronal breakdown requiring extraction

Upon obtained of informed consent, based on the tooth as the unit, it will then be randomised (1:1:1 via blocks) to either intervention arms by an independent collaborator based on the allocation sequence. The collaborator will not be involved in the study and was responsible for keeping the randomisation list. The randomisation allocation sequence will be generated using computer software.

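### The factor regression treats teeth as independent: if children contribute several correlated teeth, a child-level factor can reach p<0.05 too often (minor, conditional)

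*Combined protocol and SAP*

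**What the plan says.** Under Data Management and Analysis, the plan states: "Association studies such as factors affecting the outcome will be further evaluated using the Binary Logistic Regression". The same paragraph adds "In all analyses, the level of significance is set at" p<0.05. It names no factor and does not say whether the test is Wald or likelihood-ratio.

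Under Methodology, allocation is "based on the tooth as the unit, it will then be randomised (1:1:1 via blocks) to either intervention arms". Eligibility reads "Subject presented with at least one MIH FPM with" a qualifying lesion. It sets no upper limit and no rule of one tooth per child. The Rationale describes the condition as "affecting one to four first permanent molars". The Observation paragraph determines success or failure for each molar.

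The Sample size section counts teeth only: "Hence, the number was increased to 21 teeth per group for a total of 63 teeth". It gives no number of children. Nowhere do the documents mention within-child correlation, a random effect, estimating equations, a robust variance or the selection of one tooth per child.

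**The concern.** Ordinary logistic regression treats every row as an independent observation. A child-level factor, for example age (eligibility spans 5 to 15 years), takes the same value for all teeth of a child. If those teeth also tend to succeed or fail together, the model counts one child's information several times. The standard error for that factor is then too small, and a test run at 5% rejects more often than 5% when the factor has no effect.

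At stake is a false report that some characteristic of the child predicts success or failure. Three conditions must hold together: several teeth per child, outcomes correlated within child, and a child-level factor in the model. The documents permit all three and settle none.

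**Working it through.** **Inputs from the documents.** 63 teeth, 21 per arm; 1:1:1 allocation by tooth; alpha 0.05 (sidedness not stated, two-sided taken here). Planning success is "restoration using ART technique in MIH affected permanent molars was 98.3" per cent for glass ionomer, and for the other treatments "the success rate was assumed to be 50" per cent.

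**The plan's own figure.** For 98.3% against 50% at 90% power, with teeth independent, the pooled two-sided formula gives (1.960 × 0.619 + 1.282 × 0.516)² / 0.483² = 15.1, so 16 per group. The one-sided version gives 13. Exact power of the two-sided Pearson test is 90.1% at 13 and 92.7% at 14. The stated 14 is therefore reproduced to within two teeth; 14 × 1.5 = 21 and 21 × 3 = 63. The plan states no error rate for the logistic regression.

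**Assumptions, not in the documents.** Teeth per child, within-child correlation, and a child-level factor with no true effect.

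**Analytic check.** With m teeth per child and intraclass correlation ICC on the success/failure scale, DE = 1 + (m − 1) × ICC, and true type I error = 2 × [1 − Φ(1.96 / √DE)]. For m = 2 and ICC 0.3, DE = 1.3, 1.96 / 1.140 = 1.719, and the error is 8.6%.

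| m | ICC 0.1 | ICC 0.3 | ICC 0.5 |
|---|---|---|---|
| 1 | 5.0% | 5.0% | 5.0% |
| 1.5 | 5.6% | 6.8% | 8.0% |
| 2 | 6.2% | 8.6% | 11.0% |
| 3 | 7.4% | 12.1% | 16.6% |
| 4 | 8.6% | 15.5% | 21.5% |

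**Simulation at this trial's size.** Probit random-intercept model, 63 teeth, all followed, latent correlation 0.3 and 0.7, continuous and binary null child-level factors. At 98.3/50/50 there were two runs of 4,000 replicates per cell, with and without arm in the model. The uniform rate is (98.3 + 50 + 50) / 3 = 66%. At 50% success a latent correlation ρ corresponds to a binary correlation of (2/π) × arcsin(ρ), so 0.3 is about 0.19 and 0.7 about 0.49.

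| Teeth per child (children) | Wald, 98.3/50/50 | Likelihood ratio, 98.3/50/50 | Uniform 66%, Wald to likelihood ratio |
|---|---|---|---|
| 1 (63) | 3.4-5.0% | 5.0-6.8% | 3.9-4.3% (Wald only) |
| 1-2 (about 42) | 4.6-7.3% | 6.0-9.3% | 5.7-10.0% |
| 2 (32) | 5.0-8.6% | 5.9-10.0% | 5.6-12.1% |
| 1-4 (about 26) | 5.9-11.8% | 7.0-14.5% | 7.9-17.1% |
| 3-4 (about 18) | 5.8-14.1% | 7.0-17.2% | 9.8-21.0% |

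At latent correlation 0.1 and 98.3/50/50, Wald error is roughly 4-6%.

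**With loss.** Falling from 21 to 14 per group loses one third. If teeth are lost at random, Wald error is 4.0-6.0% with two teeth and 4.3-9.2% with 3-4. If whole children are lost, it is 4.4-7.8% and 5.6-11.6%.

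**What is not inflated.** A null tooth-level factor varying independently within child gives 3.8-5.1% (Wald) and 4.7-6.9% (likelihood ratio), as with one tooth per child. For a null arm effect at 70% success, an assumed three-arm Pearson test on teeth gives 1.8-5.6%. In one extreme setting (three teeth per child, latent correlation 0.7, blocks of 3) it falls to about 0.5%.

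**Corrected analyses of a null child-level factor, 98.3/50/50, no loss.** Plain robust variance with normal reference: 4.1-10.4%. Mancl-DeRouen: 2.5-5.8% with normal reference, 1.7-4.4% with t reference. Robust variance with t reference and K/(K − 1) scaling, K being the number of children: 2.6-7.5%, mostly near 5%. With one third lost, Mancl-DeRouen with normal reference gives 1.8-5.2%.

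**The case against.** The strongest reply is that nothing in the documents shows the problem will occur. The eligibility wording is a minimum, the one-to-four range describes the disease, and neither says how many teeth of a child will be enrolled. No factor is named, and age is only an example. At low correlation, or with two teeth per child and a third of teeth lost, the Wald test is close to nominal. Part of the likelihood-ratio excess is not clustering at all, since it reaches 6.8% with one tooth per child.

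All of this stands as a limit on size, and it is why the point is conditional and minor. It does not remove the point: the eligibility rules allow several teeth per child, and the named method is not valid for child-level factors under enrolment that the rules permit.

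A reader might infer two stronger things. One is that the treatment comparison also gains false positives. The documents do not support this, because teeth are randomised individually; a between-arm test that ignores the child is not inflated, but it can be conservative. The other is that every factor in the regression is suspect. Factors that vary independently between teeth of the same child are not inflated.

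**Conclusion.** The point holds as a minor, conditional one. If children contribute several teeth, outcomes are correlated within child, and a child-level factor is tested, the planned regression does not keep its stated 5%.

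The excess is negligible at weak correlation and modest with two teeth per child. It can reach two to four times nominal with more teeth per child and strong correlation; this is not confined to 3-4 teeth, since a mix of 1-4 also shows it. The upper ends quoted for a uniform 66% success are likelihood-ratio results. Confidence is high in the conditional statement only.

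The factor regression lies outside the stated objective, which compares treatments. Nothing here judges whether the planned goodness-of-fit and Friedman tests are suitable for comparing arms. That is a separate matter, as is the lack of a finite arm coefficient in a logistic model if the control arm has no failures.

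**What to change.** Record a child identifier with each tooth, and report the numbers of children and teeth per arm. Name the factors in advance. Fit the factor regression as a logistic GEE, or an equivalent model, clustered on child with a small-sample correction: for example Mancl-DeRouen standard errors, or a robust variance with a t reference based on the number of children. A plain robust variance with a normal reference is not enough, since it can still reach about 10%. The plan names only SPSS 26; if that version does not offer the chosen correction, state the software that will be used. Tooth-level randomisation need not change.

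The cost is SAP wording, one data field and possibly other software, with no extra patients or visits. Intervals for child-level factors widen and power falls. For an assumed binary child-level factor (69% against 31% success in the two SDF arms), power of the ordinary Wald test against the Mancl-DeRouen test (normal reference) is:

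| Teeth per child | Arm not in model | Arm in model |
|---|---|---|
| 1 | 61-62% to 58% | 71-72% to 66-67% |
| 2 | 62% to 49-56% | 69-71% to 51-58% |
| 3-4 | 58-59% to 35-46% | 65-66% to 33-46% |

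Part of the ordinary test's power comes from its inflated error. The corrected test can be slightly conservative, down to about 2% with loss. If every child contributes one tooth, a sentence saying so settles the matter.

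### If treatment arm enters the planned logistic regression, the plan's own 98.3% success rate gives a 70% chance that HVGIC has no failures and its odds ratios have no finite estimate

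*Combined protocol and SAP*

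**What the plan says.** The Data Management and Analysis section gives comparison of categorical outcomes to a chi-square goodness-of-fit test and a Friedman test. It then says that association studies, such as factors affecting the outcome, will be "further evaluated using the Binary Logistic Regression". The software is SPSS 26 and the significance level is 0.05 throughout. The section lists no factors. It does not say whether inference will be by Wald or likelihood-ratio test, and it has no rule for a group in which nobody fails.

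The Sample size section supplies the rates. It reports that GIC success "in MIH affected permanent molars was 98.3" per cent, and for the SDF and papain treatments "the success rate was assumed to be 50" per cent. The "minimum estimated sample size was calculated to be 14 teeth per intervention group", and after the allowance for dropout "the number was increased to 21 teeth per group for a total of 63 teeth".

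The Objective section sets out to compare success and failure between HVGIC alone and the two SDF arms at 6 and 12 months.

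**The concern.** Ordinary logistic regression estimates an odds ratio by maximum likelihood. If one arm has no failures, the likelihood keeps rising as that arm's log odds of failure go to minus infinity, so there is no finite estimate for any contrast with that arm. Software stops at some iteration and prints a very large coefficient with a much larger standard error. The Wald p-value is then close to 1, whatever the true difference.

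At 98.3% success the HVGIC arm is expected to have fewer than one failure, so under the design assumptions an empty failure cell is the most likely result. The contrasts lost are SDF versus HVGIC and SDF plus papain versus HVGIC, which are the ones the stated aim asks about. Without a rule in advance, the analyst would have to choose a remedy after seeing the data.

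**Working it through.** **Inputs**

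- HVGIC success 98.3%, SDF/papain success 50%, error 5%, power 90%, 14 teeth per group raised to 21 (Sample size section). Sidedness is not stated; two-sided is assumed.
- Binary success/failure outcome (Observation section and Table 1).
- Ordinary binary logistic regression (Data Management and Analysis section).
- Assumed: teeth are independent, and treatment arm is a factor in the model.

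**The plan's own figure.** Exact enumeration of the uncorrected two-sided Pearson chi-square for 98.3% versus 50% gives power 0.901 at 13 teeth per group and 0.927 at 14, so 14 meets the 90% target. The pooled normal formula gives 16. The inflation is 14 × 1.5 = 21, as stated. The rates used below are therefore the ones on which the trial was sized.

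**Chance of no HVGIC failures.** P(zero failures in n teeth) = (success rate)^n.

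| HVGIC success | n = 21 | n = 14 |
|---|---|---|
| 98.3% | 69.8% | 78.7% |
| 95% | 34.1% | 48.8% |
| 90% | 10.9% | 22.9% |
| 85% | 3.3% | 10.3% |
| 80% | 0.9% | 4.4% |

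Expected HVGIC failures at 98.3%: 21 × 0.017 = 0.36.

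**What the regression then does.** Take failures of 0/21 (HVGIC), 10/21 (SDF) and 11/21 (SDF plus papain), close to the planned rates. The ordinary maximum-likelihood fit, with arm as the factor and HVGIC as reference, gives:

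| Iterations | Log OR, SDF | Log OR, SDF + papain | SE | Wald p |
|---|---|---|---|---|
| 10 | 11.5 | 11.7 | 43 | 0.79 |
| 20 | 21.5 | 21.7 | 6,379 | 0.997 |
| 25 | 26.5 | 26.7 | 77,713 | 1.00 |

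The printed numbers depend only on where the algorithm stops. With 1/21 HVGIC failures the same model converges: log odds ratios 2.90 and 3.09, SE 1.11, Wald p 0.009 and 0.006.

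**Other methods on 0/21 versus 10/21**

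- Fisher's exact test: p = 0.0005.
- Likelihood-ratio test in the ordinary model: 2 × [−14.532 − (−23.053)] = 17.0 on 1 df, p = 0.00004.
- Firth penalised likelihood: for a two-group table this equals adding 0.5 to each cell, so OR = (10.5/11.5)/(0.5/21.5) = 39.3. The penalised likelihood-ratio p is 0.00016 and the 95% profile interval is 4.4 to about 5,200.

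**The contrast that survives.** SDF plus papain versus SDF, at 11/21 versus 10/21, has log OR = ln[(11/10)/(10/11)] = 0.19, with SE = √(1/11 + 1/10 + 1/10 + 1/11) = 0.62. Both are finite.

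**The case against.** The strongest reply is that the regression is not the trial's treatment comparison. The plan gives it a follow-on role and never names arm as a factor. It assigns the outcome comparison to other tests, and the sample size rests on a Pearson chi-square. This stands, and it limits the point to a secondary analysis. Whether the analysis section names the right chi-square test is a separate matter. Even so, the objective is to compare arms, so arm is the natural first factor in any model of what affects the outcome.

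A second reply is that 98.3% may be too high for this trial. The Sample size section itself expects much retreatment of GIC restorations. Table 1 counts marginal breakdown, new marginal caries and hypersensitivity as failures. If missing teeth were counted as failures (no such rule is stated), an empty cell would be less likely. This also stands: at 85% success or below, the chance with 21 teeth is about 3% or less. But 98.3% is the rate the plan adopts, and at 95% the chance is still one in three.

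A reader might infer that a very large arm effect would be reported as not significant. The documents do not support that. They do not commit to Wald tests, the likelihood-ratio and contingency-table tests detect the effect easily, and the 0/21 frequency would be visible in the descriptive tables the plan calls for. A reader might also infer that other sparse factor levels will fail in the same way. No factors are listed, so that cannot be shown.

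**Conclusion.** The point holds as a conditional one about a secondary analysis. If arm is a factor and HVGIC success is 98.3%, the named method has a 70% chance with 21 teeth (79% with 14) of giving no finite odds ratio and no useful Wald p-value for either comparison with HVGIC. The chance is 34% at 95% success, 11% at 90%, 3% at 85% and 1% at 80%.

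These figures treat teeth as independent; positive correlation between teeth of the same child within the arm would raise them. They do not show that the main comparison of arms fails, and 70% is not a forecast of what will happen, because it depends on a planning rate that sits uneasily with the same section's expectation of retreatment. What is lost is a usable effect estimate from ordinary logistic regression against HVGIC. The change is worth making because it is cheap and the plan's own inputs make the problem likely.

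**What to change.** In the Data Management and Analysis section:

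- Replace ordinary binary logistic regression with Firth penalised-likelihood logistic regression, reporting penalised likelihood-ratio p-values and profile-likelihood intervals. Exact logistic regression is an acceptable alternative.
- Name treatment arm as a factor, with HVGIC as the reference.
- State that Wald p-values for arm contrasts will not be reported when an arm has no failures.

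The cost is a few lines of SAP wording. It may need an SPSS add-on or a second package. Recruitment, visits and data collection do not change. The interval will still be wide when an arm has no failures (4.4 to about 5,200 in the example), which correctly reflects how little the data say about the upper limit.
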